5.2.2 Timing of Dose Administration

Trial treatment should be administered on Day 1 of each cycle after all procedures/assessments have been completed as detailed on the Trial Flow Chart (Section 6.0). Trial treatment may be administered up to 3 days before or after the scheduled Day 1 of each cycle due to administrative reasons.

All trial treatments will be administered on an outpatient basis.

Pembrolizumab will be administered as a 30 minute IV infusion (treatment cycle intervals may be increased due to toxicity as described in Section 5.2.1.2). Sites should make every effort to target infusion timing to be as close to 30 minutes as possible. However, given the variability of infusion pumps from site to site, a window of -5 minutes and +10 minutes is permitted (i.e., infusion time is 30 minutes: -5 min/+10 min).

The Pharmacy Manual contains specific instructions for pembrolizumab dose calculation, reconstitution, preparation of the infusion fluid, and administration.

5.2.3 Trial Blinding/Masking

This is an open-label trial; therefore, the investigator and subject will know the treatment administered.

5.3 Randomization or Treatment Allocation

This is not a randomized trial. All patients will receive treatment.

5.4 Stratification

There will not be up-front stratification.

5.5 Concomitant Medications/Vaccinations (allowed & prohibited)

Medications or vaccinations specifically prohibited in the exclusion criteria are not allowed during the ongoing trial. If there is a clinical indication for one of these or other medications or vaccinations specifically prohibited during the trial, discontinuation from trial therapy or vaccination may be required. The investigator should discuss any questions regarding this with [name]. The final decision on any supportive therapy or vaccination rests with the investigator and/or the subject's primary physician. However, the decision to continue the subject on trial therapy or vaccination schedule requires the mutual agreement of the Investigator and the subject.

External beam radiation therapy is permitted on this study. Its use should be disclosed and described (dose, number of areas, number of treatments, treatment dates and response) as a Concomitant Therapy in clinical report forms. There are no data regarding the simultaneous use of radiation and pembrolizumab. Therefore, if radiation is needed, the pembrolizumab should be held one week prior to radiation and for 2 weeks after radiation therapy.

Subjects eligible for this study are progressing on enzalutamide and must continue the enzalutamide while on this study. However, enzalutamide may be held for adverse events thought to be related to enzalutamide. If a subject is off of enzalutamide for longer than 30 consecutive days, either directly prior to starting the study or after enrollment, the principal investigator needs to be alerted.

5.5.1 Acceptable Concomitant Medications

All treatments that the investigator considers necessary for a subject's welfare may be administered at the discretion of the investigator in keeping with the community standards of medical care. All concomitant medication will be recorded on the case report form (CRF) including all prescription, over-the-counter (OTC), herbal supplements, and IV medications and fluids. If changes occur during the trial period, documentation of drug dosage, frequency, route, and date may also be included on the CRF.

All concomitant medications received within 28 days before the first dose of trial treatment and 30 days after the last dose of trial treatment should be recorded. Concomitant medications administered after 30 days after the last dose of trial treatment should be recorded for SAEs and ECIs as defined in Section 7.2.

As noted above, external beam radiation is permitted, and enzalutamide should be continued. Radium-223, strontium and samarium are prohibited.

5.5.2 Prohibited Concomitant Medications

Subjects are prohibited from receiving the following therapies during the Screening and Treatment Phase (including retreatment) of this trial:

- Anti-cancer systemic chemotherapy, hormone therapy or biological therapy
- Immunotherapy not specified in this protocol
- Radiopharmaceuticals such as Radium-223, strontium, and samarium
- Investigational agents other than pembrolizumab
- Live vaccines within 30 days prior to the first dose of trial treatment and during active treatment. Examples of live vaccines include, but are not limited to, the following: measles, mumps, rubella, chicken pox, yellow fever, rabies, BCG, and typhoid (oral) vaccine. Seasonal influenza vaccines for injection are generally killed virus vaccines and are allowed; however intranasal influenza vaccines (e.g. Flu-Mist®) are live attenuated vaccines, and are not allowed.
- Glucocorticoids for any purpose other than to modulate symptoms from an event of clinical interest of suspected immunologic etiology. The use of physiologic doses of corticosteroids may be approved after consultation with the Sponsor.
- Agents that can affect PSA, other than LHRH-agonists and enzalutamide. Examples of these agents include bicalutamide, flutamide, nilutamide, abiraterone, prednisone, and herbal agents such as PC-SPES and saw palmetto.
- Denosumab (also known as Prolia and Xgeva) is prohibited because it can be immunosuppressive.

Subjects who, in the assessment by the investigator, require the use of any of the aforementioned treatments for clinical management should be removed from the trial. Subjects may receive other medications that the investigator deems to be medically necessary.

The Exclusion Criteria describes other medications which are prohibited in this trial.

There are no prohibited therapies during the Monitoring Phase.

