5.6.1.1 Supportive Care Guidelines for Immune-related Adverse Events (irAEs)

Events of clinical interest of a potential immunologic etiology (irECIs) may be defined as an adverse event of unknown etiology, associated with drug exposure and is consistent with an immune phenomenon. irAEs may be predicted based on the nature of the pembrolizumab compound, its mechanism of action, and reported experience with immunotherapies that have a similar mechanism of action. Special attention should be paid to AEs that may be suggestive of potential irAEs. An irAE can occur shortly after the first dose or several months after the last dose of treatment.

If an irAE is suspected, efforts should be made to rule out neoplastic, infectious, metabolic, toxin or other etiologic causes prior to labeling an adverse event as an irAE. Information on how to

identify and evaluate irAEs has been developed and is included in the Event of Clinical Interest and Immune-Related Adverse Event Guidance Document. See Section 12.6. Subjects who develop a Grade 2 or higher irAE should be discussed immediately with the Sponsor.

Recommendations to managing irAEs not detailed elsewhere in the protocol are detailed in Table 5.

Table 5 General Approach to Handling irAEs

irAE	Withhold/Discontinue Pembrolizumab?	Supportive Care
Grade 1	No action	Provide symptomatic treatment
Grade 2	May withhold pembrolizumab	Consider systemic corticosteroids in addition to appropriate symptomatic treatment
Grade 3 and Grade 4	Withhold pembrolizumab Discontinue if unable to reduce corticosteroid dose to < 10 mg per day prednisone equivalent within 12 weeks of toxicity	Systemic corticosteroids are indicated in addition to appropriate symptomatic treatment. May utilize 1 to 2 mg/kg prednisone or equivalent per day. Steroid taper should be considered once symptoms improve to Grade 1 or less and tapered over at least 4 weeks.

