8.1 Primary and Secondary Endpoints

Primary endpoint: PSA response, defined by a PSA decrease of at least 50% confirmed by a second measurement at least 3 weeks later.

Secondary endpoints:

- % change in PSA
- Immunological parameters, including leukocytes, lymphocytes (CD8+, CD4+, and B cells), and macrophages in prostate tissue at diagnosis (if original biopsy is available) and pre-treatment.
- Immunohistochemistry for PD-1, PD-L1 and PD-L2 in prostate tissue at diagnosis (if original biopsy is available) and pre-treatment
- Circulating tumor cells (CTCs) (binary variable)
- Changes in T cell numbers, activation, and phenotype as measured in PBMC at diagnosis and throughout therapy, including T effector/memory panel (CD45, CD3, CD8, CCR7, CD45RA, CD45RO, CD69, CD44, CD62L), T regulatory panel (CD45, CD3, CD4, FoxP3, CD25, CD127, CD69, CD44), T help panel (CD45, CD3, CD4, CD45RA, CD45RO, CD69, CD44, CD62L), and cytokine propensity of the above T cell subsets (IFN- γ , IL-2, IL-4, IL-12, IL-13, IL-10, IL-18, TNF- α , TGF- β , IL-17)
- Systemic inflammatory markers: Serum IL-8, IL-6, IL-1, TNF and TGF-beta
- Objective disease response by radiographs
- Overall survival
- PSA progression free survival where the definition of progression will be PSA progression per Prostate Cancer Working Group 2 criteria. If there is a decline from baseline, progression is an increase in PSA that is 25% and 2 ng/ml above the nadir, which is confirmed by a second value 3 or more weeks later (i.e., a confirmed rising trend)

- DNA mutations.

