8.3 Sample Size Computation

Patients with PSA progression on treatment are extremely unlikely to have a PSA response without a change in therapy. If 25% of subjects treated with pembrolizumab upon progression with enzalutamide have a PSA response, this therapy would be worthy of further study. Using a null hypothesis of 5% and alternate hypothesis of 25%, 25 evaluable patients are needed with 90% power and a one-sided alpha of 0.05. To account for potential drop-out, we will enroll 28 subjects.

We propose to add 30 additional subjects to this study (for a total of 58) to better evaluate the association between PSA responses and candidate risk factors (MSI and PD-L1 expression with other immunological parameters), and to build a prognostic model. The proposed sample size will achieve 80% power to detect AUC of 0.85 against AUC of 0.6 using two-sided z test at 5% significance level. We understand that it is not guaranteed that a predictive model with good predictive ability can be constructed, because both MSI and PD-L1 expressions are relatively rare. However, the collected data and analysis will be clinically valuable to help us determine whether a future larger study is worthy. . In the initial study, we did biopsies on any subject that had a

metastatic lesion that could be biopsied, but subjects were not required to have a lesion that could be biopsied. We are doing biopsies on all 30 additional patients along with the tests we did on earlier participants.

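### PSA values drawn on or soon after systemic steroids are not separated in the primary endpoint, although section 5.5.2 lists prednisone as an agent that can affect PSA

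*Combined protocol and SAP*

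**What the plan says.** Section 5.5.2 lists what is prohibited in the Screening and Treatment Phase, including retreatment. One bullet covers "Agents that can affect PSA, other than LHRH-agonists and enzalutamide. Examples of these agents include bicalutamide, flutamide, nilutamide, abiraterone, prednisone" and some herbal agents. Another bullet in the same list prohibits "Glucocorticoids for any purpose other than to modulate symptoms from an event of clinical interest of suspected immunologic etiology", which leaves glucocorticoids for immune-related events permitted. The section then says that subjects who need any listed treatment should leave the trial, and closes with "There are no prohibited therapies during the Monitoring Phase". Section 5.5, by contrast, keeps medications named in the exclusion criteria off limits while the trial is ongoing.

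The toxicity sections lead to steroids:
- **Section 5.6.1** calls for systemic corticosteroids in enterocolitis above Grade 2 and in persistent Grade 2 enterocolitis, with a taper of at least a month.
- **Section 5.6.1.1, Table 5** says of Grade 3 and 4 events "May utilize 1 to 2 mg/kg prednisone or equivalent per day", with a taper of at least 4 weeks. Pembrolizumab stops only if the steroid dose cannot be brought below 10 mg per day within 12 weeks.
- **Section 5.6.1.2** indicates systemic corticosteroids for pneumonitis from Grade 2 and allows a return to treatment after Grade 2.
- **Appendix 12.6** gives further courses, most with tapers of no less than 4 weeks.

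Section 8.1 defines the primary endpoint as "PSA response, defined by a PSA decrease of at least 50% confirmed by a second measurement at least 3 weeks later". Section 8.2 tests the response proportion against 0.05 with a one-sample binomial test. Neither section mentions PSA values drawn during or after steroid treatment.

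**The concern.** The protocol itself treats prednisone as able to disturb PSA, and its own toxicity guidance puts some subjects on prednisone or an equivalent. PSA continues to be drawn. A new anti-cancer therapy moves a subject to survival follow-up (7.1.1.5.3), but a steroid course for toxicity does not.

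The trial has one arm. Its 5% null rests on the argument in 4.2.3.1 and 8.3 that men progressing on treatment hardly ever respond by PSA unless therapy changes. If steroids given for pembrolizumab toxicity lowered PSA by half in some men, the null rate would no longer be 5%, and there is no control group in which to see it.

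The expansion to 58 subjects exists to relate immunological parameters to PSA response. Steroids follow immune toxicity, so a steroid-related fall could produce an association between immune measures and response that does not reflect tumour control.

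**Working it through.** **1. The plan's own figure.** Inputs from section 8.3: "Using a null hypothesis of 5% and alternate hypothesis of 25" percent, and "25 evaluable patients are needed with 90% power and a one-sided alpha of 0.05". The exact upper tail is P(X ≥ r) = Σ C(n,k) p^k (1−p)^(n−k), summed over k = r to n.
- n = 25, p = 0.05: P(X ≥ 3) = 0.127 and P(X ≥ 4) = 0.034, so the test rejects at 4 responders.
- n = 25, p = 0.25: P(X ≥ 4) = 0.904.

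The figure of 25 reproduces and is the smallest n with 90% exact power. It is not in dispute.

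**2. The current size.** Sections 1.0 and 8.3 give a total of 58. The plan restates no rejection rule for 58, so I apply the same one-sided 0.05 level: P(X ≥ 6) = 0.069 and P(X ≥ 7) = 0.025. The threshold is 7 responders.

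**3. Effect of a raised null rate (assumed).** The documents give neither the share of subjects who receive systemic steroids nor the chance that steroids alone produce a confirmed 50% fall. Taking 10-20% for each, the added rate is 0.10 × 0.10 = 1 point up to 0.20 × 0.20 = 4 points. The no-effect rate becomes 6-9%.

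| n | rejects at | false-positive rate at 5% | at 6% | at 9% |
|---|---|---|---|---|
| 25 | ≥ 4 | 3.4% | 6.0% | 18.3% |
| 28 | ≥ 4 | 4.9% | 8.4% | 24.2% |
| 58 | ≥ 7 | 2.5% | 5.8% | 26.5% |

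If steroids can add responses only among the 95% who would not respond anyway, the upper rate is 0.05 + 0.95 × 0.04 = 8.8%. The false-positive rate is then 17.3% at n = 25 and 24.7% at n = 58, so the picture is unchanged.

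**4. Does confirmation protect the endpoint?** The flow chart draws PSA at each 3-week cycle, 3 weeks after cycle 4, and then every 6 weeks in monitoring.
- Draws 3 weeks apart: a taper of 4 weeks can cover both.
- Draws 6 weeks apart: 6 − 4 = 2, so about 2 weeks of steroid before a minimum taper would be needed to cover both. Table 5 tolerates up to 12 weeks before the dose must be low, and appendix 12.6 has tapers of 6 to 8 weeks and of 45 to 60 days. Spanning is therefore possible, but not automatic.

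**5. Other possible safeguards.** The Week 12 rule (7.1.2.6, 7.1.2.11) concerns progression, not response. Section 7.1.5.2 rules out official response assessment during the first four doses but says nothing about later values.

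**6. How much hangs on one response.** At 58, 7 responders give P = 0.025 and 6 give P = 0.069. Section 4.1.1 reports seven responses with the 38th subject through four cycles. If all seven met the endpoint definition, which is not stated, 7/38 gives P = 0.0025, 6/38 gives 0.011, 5/38 gives 0.040 and 4/38 gives 0.12. Three would have to be reclassified to lose significance.

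**7. PSA progression-free survival.** Section 8.1 requires a rise of 25% and of 2 ng/ml above nadir. The threshold is the larger of 1.25 × nadir and nadir + 2, and both fall as the nadir falls. A steroid-related fall could postpone progression while it lasts, or lower the nadir so that a later rise meets the threshold sooner.

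**The case against.** The strongest objection is that the mechanism is not in the documents. Section 5.5.2 says only that prednisone can affect PSA. A fall is inferred from its place beside anti-androgens and abiraterone; size and duration are not given, and both rates in the calculation are assumed. That stands, and it limits what can be claimed.

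Second, section 5.5.2 says subjects who need a listed treatment should leave the trial, so exposed values might never arise. This does not settle the matter. The removal sentence conflicts with the glucocorticoid exemption in the same list and with Table 5, which lets a subject on steroids resume pembrolizumab. The flow chart also draws PSA at the discontinuation and safety visits, and nothing excludes those values. It is true that several severe-event paths stop pembrolizumab for good, after which 7.1.5.4 specifies imaging rather than PSA, so the exposure is narrower than the list of steroid indications suggests.

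Third, the change in therapy mentioned in 8.3 most naturally means a change in anti-cancer treatment. That is fair, but the null rate is used as a number, and anything that raises it matters.

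A reader might infer more than the documents support:
- That the plan says on-steroid values count. It is silent, and the definition takes any confirmed fall.
- That a minimum 4-week taper routinely covers both PSA draws. With draws 6 weeks apart it does not.
- That one steroid-related response would overturn the trial. That is so only when the count sits on the threshold.
- That steroids would lengthen PSA progression-free survival. The direction is indeterminate.

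**Conclusion.** The gap is real. The protocol names prednisone as able to affect PSA, provides for its use, and has no rule for the PSA values that result. A steroid-related fall could be counted as a pembrolizumab response, and the confirmation rule does not reliably prevent it.

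The size is conditional. The false-positive figures show what a null rate of 6-9% would do; that range is an assumption, not an estimate of what steroids do. The reported responses may well leave the main conclusion intact, but the response rate and the biomarker associations could still be affected. The documents do not show that bias has occurred, and the sample size calculation is sound on its own terms.

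This is a cheap improvement rather than a flaw that undermines the design. Confidence is moderate.

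**What to change.** Keep the primary analysis as it is. In sections 8.1 and 8.2:
- Flag every PSA value drawn from the start of any systemic corticosteroid, or other agent on the PSA-affecting list in 5.5.2, until a fixed, prespecified interval after it stops.
- Add a prespecified sensitivity analysis of PSA response in which both the qualifying and the confirming value must be unflagged.
- Report the number of responses that depend on flagged values.
- Run the same sensitivity analysis for PSA progression-free survival and the biomarker models.

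Make start and stop dates of these agents mandatory on the CRF for as long as PSA is collected. Section 5.5.1 makes recording of dates optional when medication changes, and more than 30 days after the last dose it asks for concomitant medications only for SAEs and ECIs. Dated capture of other steroid use in monitoring is therefore not assured.

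Reconcile the two bullets, the removal sentence and the Monitoring Phase sentence in 5.5.2 with each other, with 5.5, and with 5.6.1, 5.6.1.1, 5.6.1.2 and 12.6. No clinical rule is proposed here.

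The cost is a small CRF change, SAP wording and one extra analysis for each affected outcome. The downside is that a true response that began on steroids is not counted in the sensitivity analysis, so its rate may understate activity. It should be read beside the primary result, not in place of it.

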5.1.3 Subject Exclusion Criteria

The subject must be excluded from participating in the trial if the subject:

1. Is currently participating in or has participated in a study of an investigational agent or using an investigational device within 4 weeks of the first dose of treatment.
2. Has a diagnosis of immunodeficiency or is receiving systemic steroid therapy or any other form of immunosuppressive therapy within 7 days prior to the first dose of trial treatment. The use of physiologic doses of corticosteroids may be approved after consultation with the Sponsor.
3. Has had a prior monoclonal antibody within 4 weeks prior to study Day 1 or who has not recovered (i.e., \leq Grade 1 or at baseline) from adverse events due to agents administered more than 4 weeks earlier. **Denosumab is a prohibited medication** on study and for 4 weeks prior to day 1.
4. Has had chemotherapy for castration-resistant disease. Chemotherapy for castration-sensitive disease is permitted.

5. Has had prior chemotherapy, targeted small molecule therapy, or radiation therapy within 2 weeks prior to study Day 1 or who has not recovered (i.e., \leq Grade 1 or at baseline) from adverse events due to a previously administered agent.
 - Note: Subjects with \leq Grade 2 neuropathy are an exception to this criterion and may qualify for the study.
 - Note: If subject received major surgery, they must have recovered adequately from the toxicity and/or complications from the intervention prior to starting therapy.
6. Has a known additional malignancy that is progressing or requires active treatment. Exceptions include basal cell carcinoma of the skin, squamous cell carcinoma of the skin, or in situ bladder cancer that has undergone potentially curative therapy.
7. Has known brain metastases and/or carcinomatous meningitis.
8. Has a history of seizure
9. Has allergy to enzalutamide

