10. Has an active autoimmune disease requiring systemic treatment within the past 3 months or a documented history of clinically severe autoimmune disease, or a syndrome that requires systemic steroids or immunosuppressive agents. A severe autoimmune disease is one that requires a significant medical intervention such as hospitalization. Subjects with vitiligo or resolved childhood asthma/atopy would be an exception to this rule. Subjects that require intermittent use of bronchodilators or local steroid injections would not be excluded from the study. Subjects with hypothyroidism stable on hormone replacement or Sjorgen's syndrome will not be excluded from the study.
11. Has a history of (non-infectious) pneumonitis that required steroids or current pneumonitis. Has an active infection requiring systemic therapy.
12. Has a history or current evidence of any condition, therapy, or laboratory abnormality that might confound the results of the trial, interfere with the subject's participation for the full duration of the trial, or is not in the best interest of the subject to participate, in the opinion of the treating investigator.
13. Has known psychiatric or substance abuse disorders that would interfere with cooperation with the requirements of the trial.
14. Has received prior therapy with an anti-PD-1, anti-PD-L1, anti-PD-L2, anti-CD137, or anti-Cytotoxic T-lymphocyte-associated antigen-4 (CTLA-4) antibody (including ipilimumab or

any other antibody or drug specifically targeting T-cell co-stimulation or checkpoint pathways). Previous treatment with sipuleucel-T is permitted.

15. Has plans to receive cytotoxic chemotherapy, immune checkpoint inhibitors (eg CTLA-4 blockade), sipuleucel-T, radiopharmaceuticals, abiraterone or other experimental therapy during this study period.
16. Has a known history of Human Immunodeficiency Virus (HIV) (HIV 1/2 antibodies).
17. Has known active Hepatitis B (e.g., HBsAg reactive) or Hepatitis C (e.g., HCV RNA [qualitative] is detected).
18. Has received a live vaccine within 30 days prior to the first dose of trial treatment.
19. Has rapid progression of visceral disease and, thus is a candidate for docetaxel. This determination will be at the discretion of the treating physician.

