7.1.1.5.3 Subsequent Anti-Cancer Therapy Status

The investigator or qualified designee will review all new anti-neoplastic therapy initiated after the last dose of trial treatment. If a subject initiates a new anti-cancer therapy within 30 days after the last dose of trial treatment, the 30 day Safety Follow-up visit must occur before the first dose of the new therapy. Once new anti-cancer therapy has been initiated the subject will move into survival follow-up.

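### Section 5.5.2 lifts all drug prohibitions in the Monitoring Phase, in conflict with 5.5, 5.5.1 and exclusion criterion 3, and 8.1 has no rule for PSA values taken under PSA-affecting agents

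*Combined protocol and SAP*

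**What the plan says.** Section 5.5.2 limits its list to certain phases: "Subjects are prohibited from receiving the following therapies during the Screening and Treatment Phase (including retreatment) of this trial". The list includes glucocorticoids (except for immune-related events), denosumab, and "Agents that can affect PSA, other than LHRH-agonists and enzalutamide". Its examples of the last group are bicalutamide, flutamide, nilutamide, abiraterone, prednisone, PC-SPES and saw palmetto. The section closes with "There are no prohibited therapies during the Monitoring Phase".

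Other sections set limits without a Monitoring exception:

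- Section 5.5: "Medications or vaccinations specifically prohibited in the exclusion criteria are not allowed during the ongoing trial".
- Section 5.1.3, criterion 3, prohibits denosumab "on study and for 4 weeks prior to day 1".
- Section 5.5.1: "Radium-223, strontium and samarium are prohibited".
- Section 5.1.3, criterion 15, excludes men who plan chemotherapy, checkpoint inhibitors, "sipuleucel-T, radiopharmaceuticals, abiraterone or other experimental therapy during this study period". This concerns plans at entry, but 5.5 carries excluded drugs forward.

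One safeguard exists, in 7.1.1.5.3: "Once new anti-cancer therapy has been initiated the subject will move into survival follow-up".

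Section 8.1 defines the primary endpoint as a PSA fall of at least 50%, confirmed at least 3 weeks later. It sets no time window and has no rule on concomitant agents.

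**The concern.** The trial has one arm. Sections 4.2.3.1 and 8.3 justify the 5% null rate by arguing that a man whose PSA is progressing will very rarely show a PSA response unless his therapy changes. A concomitant agent that lowers PSA is such a change, and it is not pembrolizumab. If that agent is permitted when a response is being read or confirmed, and the endpoint definition ignores it, the response is credited to pembrolizumab.

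The response rate and its interval, PSA progression-free survival, and the responder label used in the predictive models of 8.2 would all carry the error. Separately, no washout is stated before retreatment, so immunosuppressive drugs could be taken shortly before the retreatment blood samples.

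**Working it through.** **1. Which agents are in conflict.**

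- Denosumab: barred on study by criterion 3, unrestricted in Monitoring by 5.5.2. Direct conflict. Monitoring is on study, since the flow chart schedules visits and PSA every 6 weeks.
- Radium-223, strontium, samarium: barred in 5.5.1 with no phase limit, unrestricted in Monitoring by 5.5.2. Direct conflict.
- Abiraterone: named in criterion 15 and so carried forward by 5.5. Conflict with 5.5.2.
- Systemic steroids: named in criterion 2, but only for the 7 days before first dose. How far 5.5 carries this forward is unclear.
- Bicalutamide, flutamide, nilutamide, PC-SPES, saw palmetto: in no exclusion criterion. There is no contradiction. The issue is that the endpoint does not account for their permitted use.

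**2. When PSA is read.** Doses fall at weeks 0, 3, 6 and 9. The post-first-course visit is 3 weeks after cycle 4, so 9 + 3 = week 12. Section 7.1.5.2 makes no official response assessment during the four doses. The next scheduled PSA is 6 weeks later, 12 + 6 = week 18, in Monitoring. Under 7.1.2.11, PSA progression ignores values before week 12, so until retreatment it is mostly read in Monitoring too.

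**3. Who stays under PSA follow-up.** A new anti-cancer therapy moves a man to survival follow-up (7.1.1.5.3, 7.1.5.4.1). That covers abiraterone or chemotherapy and, on an ordinary reading, antiandrogens. It does not clearly cover prednisone for symptoms, herbal agents or denosumab. Section 5.5.2 calls denosumab immunosuppressive and does not name it among the PSA-affecting agents, so its relevance is to retreatment and the correlative samples.

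**4. Whether exposure would be recorded.** Section 5.5.1 requires full recording to 30 days after the last dose, then only for SAEs and ECIs, and makes dates optional. Week 18 is 18 - 9 = 9 weeks, or 63 days, after dose four: 33 days beyond that limit. The flow chart does review concomitant medications at the 6-weekly Monitoring visits, so the documents are not aligned.

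**5. Retreatment.** The 7-day and 4-week washouts in criteria 2 and 3 refer to the first dose or Day 1. Eligibility is checked only at screening. Before retreatment the plan asks for laboratory tests, imaging and, where safe, a biopsy. No drug washout is stated.

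**6. The plan's sample size.** Exact binomial, 5% against 25%, one-sided 0.05: at n=25, reject at 4 or more responders; alpha = P(X≥4 | 0.05) = 0.0341 and power = P(X≥4 | 0.25) = 0.9038. At n=24 the power is 0.885. The stated 25 reproduces.

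**7. Illustration of sensitivity.** Suppose a fraction q of men take a PSA-lowering agent in Monitoring and a fraction r of those have a qualifying fall. The no-effect rate becomes 0.05 + 0.95·q·r. Neither q nor r is in the documents. With q = 0.10 and r = 0.10 to 0.30:

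- 0.05 + 0.95 × 0.10 × 0.10 = 0.0595
- 0.05 + 0.95 × 0.10 × 0.30 = 0.0785

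| n | Reject at | Alpha at 5% | At 5.95% | At 7.85% |
|---|---|---|---|---|
| 25 | 4 | 0.034 | 0.058 | 0.128 |
| 28 | 4 | 0.049 | 0.082 | 0.174 |
| 58 | 7 | 0.025 | 0.056 | 0.168 |

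One reclassified man moves 3/28 (p = 0.163) to 4/28 (p = 0.049). That holds for any misclassified response and is not evidence about this route in particular.

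**The case against.** Monitoring is off pembrolizumab, and a lighter rule there may be deliberate. That is fair, and for agents in no exclusion criterion the lighter rule contradicts nothing. It does not resolve the conflict over denosumab and radiopharmaceuticals, nor supply the missing endpoint rule.

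A reader might infer that every response is exposed because confirmation always falls in Monitoring. The documents do not support this. PSA is drawn at each cycle, 8.1 sets no start week, and the exclusion of values before week 12 is for progression only. A fall at cycle 3 could be confirmed at cycle 4 or week 12. Section 7.1.5.2 leaves this ambiguous, not settled.

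A reader might also take the table above as the trial's actual type I error. It is not. The formula models new responses caused wholly by another drug. Where a 50% fall already existed at week 12 and a later drug only helps confirm it, the inflation applies to that smaller group. The most potent agents are largely removed by 7.1.1.5.3. In addition, 4.1.1 already reports seven responses when the 38th subject had completed four cycles, so rejection of the null may not turn on one man.

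The retreatment harm is limited: 8.2 names no confirmatory analysis of samples drawn before retreatment.

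**Conclusion.** The conflict between 5.5.2 and 5.5, 5.5.1 and criterion 3 is explicit and in current text. The gap in 8.1 is also real: as written, a PSA fall read or confirmed under an agent that the protocol lists as affecting PSA counts as a pembrolizumab response.

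The exposed group is men whose response is first seen or confirmed from week 12 on, while they take prednisone, a herbal agent or another listed drug that does not trigger survival follow-up. The size of any bias cannot be computed from the documents. The false-positive rates of about 6% to 17% depend entirely on the assumed 10% use and 10-30% effect, and show only that the test is sensitive to small shifts in the null rate.

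It would also be wrong to assume that the data to apply a rule after the fact are assured, because 5.5.1 does not require dated recording at week 18. Severity: should-fix, not must-fix.

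**What to change.** 1. **Reconcile.** The sponsor should reconcile 5.1.3 (criterion 3), 5.5, 5.5.1 and 5.5.2, state which rule applies in Monitoring, and state whether the Day 1 washouts apply before retreatment cycle 1. Which clinical rule to adopt is for the sponsor.

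2. **Endpoint rule in 8.1.** For the primary analysis, a PSA response is not established or confirmed by values drawn while a man is taking a listed PSA-affecting agent, or within a sponsor-defined period after it. State in advance how glucocorticoids given for immune-related events are handled. Sections 5.5.2, 5.6.1 and 5.6.1.1 allow or direct them, so an open-ended rule voiding all PSA values after the first such dose would disqualify men treated as the protocol intends. Report response and PSA progression-free survival both with and without the rule as a sensitivity analysis, because censoring at such drugs may be informative.

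3. **Recording.** Amend 5.5.1 so that start and stop dates of listed agents are collected through Monitoring, at the 6-weekly medication reviews already in the flow chart.

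Cost: a few sentences, a little more recording, and a date check in the endpoint derivation. The reported response rate may be slightly lower.
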